Using validated human laboratory paradigms, the proposed study will break new ground by determining whether sweet flavored cigarillos are more rewarding and reinforcing (relative and absolute) than non-flavored cigarillos among young adults. We anticipate that young adults will have a greater hedonic response to sweet flavored versus non-flavored cigarillos (greater subjective rewarding value), increased motivation to consume sweet flavored versus non-flavored cigarillos (greater relative reinforcing value), and greater consumption of sweet flavored versus non-flavored cigarillos (absolute reinforcing value). These three hypotheses will be tested across three separate laboratory visits among 86 young adults (ages 18-24 years old) who have previously smoked \geq 10 cigarillos in their lifetime. We will examine whether these indices of abuse liability remain significant while controlling for other factors that may underlie the preference for flavoring. This approach will enable us to provide evidence for the impact of sweet flavored cigarillos on subjective, objective, and behavioral outcomes among young adults.

3 Study Objectives

Primary Aim: To determine whether the subjective rewarding value, the relative reinforcing value, and the absolute reinforcing value of sweet flavored cigarillos are greater than that of non-flavored cigarillos among young adults.

- H1.** Young adults will report greater subjective rewarding value from a sweet flavored versus a non-flavored cigarillo.
- H2.** Young adults will “work harder” for sweet flavored cigarillo puffs than non-flavored cigarillo puffs (i.e., higher relative reinforcing value) as measured by a relative reinforcement choice task.
- H3.** Sweet flavored cigarillos will have higher absolute reinforcing value for young adults than non-flavored cigarillos as measured by a greater number of flavored cigarillo puffs during an ad-libitum session.

Young adulthood is a critical developmental period for the onset of regular tobacco use and the establishment of lifelong use. This will be the first study to: (1) examine the rewarding and reinforcing value (both relative and absolute) of sweet cigarillo flavoring; (2) control for other

CONFIDENTIAL

This material is the property of the University of Pennsylvania. Do not disclose or use except as authorized in writing by the study sponsor

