4.2 Study Duration

Recruitment/enrollment is anticipated to begin in August 2021 and will continue for 18 months. We estimate that up to 86 participants will have completed the study by February 2023. Visits 1-3 will be completed within a 2-3 week time period. Each participant will be considered “active” until they have completed all three laboratory visits.

4.3 Laboratory Visit 1

Participants will arrive at the BBL at approximately 1:00PM. Eligible participants will document their tobacco use that day (number, time, type) and complete lifetime and past 30 day measures of cigarillo use (flavored, non-flavored, preference), tobacco use history (e.g., cigarette smoking and menthol status), as well as baseline measures of marijuana use, depression, sensation-seeking, cigarillo risk beliefs, exposure to cigarillo flavor marketing, and demographics. Participants will provide a carbon monoxide (CO) sample and a urine sample to conduct urine cotinine analysis.

Subjective rewarding value of cigarillo flavoring. Participants will be exposed to three cigarillos. Participants who are eligible and elect to participate in the study will be required to use the study-provided cigarillos during this portion of the visit in our smoking lab. One cigarillo will be non-flavored, meaning no characterizing flavors were added to the tobacco. Two will contain sweet flavoring (fruit and cream). All three will have the same characteristics, only differing by flavor. Participants will take 2 puffs from the non-flavored cigarillo, the fruit-flavored cigarillo, and the cream-flavored cigarillo. The exposure to the three cigarillos will be separated by 20 minutes each, and the order of the three exposures will be counterbalanced. Order will be stratified by sex and smoking status. After each of the three cigarillo exposures, participants will complete measures of subjective reward. Visit 1 will occur in the afternoon versus the morning to increase the likelihood that participants who smoke cigarettes smoke normally throughout the day and can rate flavoring/no flavoring in the absence of significant withdrawal symptoms. After Visit 1, participants will be scheduled for Visit 2. Participants who use tobacco (e.g., combustible cigarettes, e-cigarettes, cigars, blunts) or combustible marijuana will be given instructions to abstain from tobacco products and combustible marijuana 10 hours prior to BBL Visit 2.

CONFIDENTIAL

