event utilizing the following severity scale: 0 (None=No Concerns), 1 (Mild=Issue does not interfere with usual daily activities), 2 (Moderate=Issue does interfere with some activities), and 3 (Severe=No normal activities are possible). See section 8.2.1: AE Collection Methods for further details.

Carbon Monoxide (CO) will be measured using a Vitalograph CO monitor (Lenexa, KS). A CO > 5 is indicative of combustible cigarette smoking. At the start of visits 2 and 3, 10-hour tobacco abstinence will be assessed via CO < 10 or 50% of the CO value measured at Visit 1.

Urine Cotinine will be measured using a test strip kit that detects the presence of cotinine in a urine sample along three detection levels: low, medium, and high. The testing kit indicates the presence and amount of cotinine measured in the urine, which is a product of nicotine metabolism with sensitivities of 50 ng/mL (low concentration), 200 ng/mL (medium concentration), and 600 ng/mL (high concentration). Participants will provide a urine sample for cotinine analysis with the expectation that cotinine level will be at least one tier lower than cotinine level at Visit 1; participants already measuring in the lowest tier are expected to remain there.

Concomitant Medications: At Laboratory Visit 1, participants will be asked to list all medications (prescription or non-prescription) and NRTs currently taken and/or recently discontinued (within the past 14 days) as a baseline collection. All information will be collected on a Concomitant Medication Log that will be maintained within the participant's study chart. At every subsequent in-person visit, participants will be asked if they have taken any additional medications (prescription or non-prescription), NRTs, and/or changed the dosage or stopped taking any previously reported medications since their last in-person visit. Participants who report taking contraindicated medication(s) over the course of the study period may only remain eligible if the Principal Investigator determine that the contraindicated medication(s) did not impact the study design, data quality, and/or participant safety and welfare.

7.4.2 Covariates – All Measured at Laboratory Visit 1

Demographics. Sex, age, education and employment will be measured at baseline. Available research suggests that women are more likely than men to use flavored cigarillos [8]. Cigarillo use history (number, flavor preference) will be included in the statistical models.

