Risk perceptions of flavored cigarillo use (e.g., impact of flavor on risk and addictiveness) will be measured with six Likert-style items derived from previous and ongoing research (0=not at all to 6=extremely). The Center for Epidemiologic Studies **Depression** Scale (CES-D) is a 20-item Likert- style measure with high internal consistency ($\alpha > .85$), and correlates with clinical ratings of depression severity. The CES-D has been used in adolescent and young adult tobacco studies. Young adults who use cigars such as cigarillos report higher levels of depression symptoms compared to those who do not use cigarillos. Flavoring appears to enhance the mood of young adults who use cigarillos. As such, we will not screen out for elevated depression symptoms. We will measure them and include them as a covariate in the statistical models as depression symptoms may underlie flavor preference. **Sensation seeking** will be measured with the 8-item Brief Sensation Seeking Scale (1=strongly disagree to 5=strongly agree) given its associations with little cigar and cigarillo use [47,100,150,151]. **Exposure to flavor-related advertising and marketing practices** will be measured with 9 items adapted from PATH and previous research. These items evaluate the source (e.g., Internet, social media, retail stores) and type (e.g., giveaways, direct mail and e-mail coupons, links to on-line vendors, branded merchandise, celebrity endorsement, music event sponsorship) of exposure to flavored cigarillo promotions.

Standard epidemiological items will measure lifetime and current use (monthly, weekly, daily, and rate) of **other tobacco products** such as combustible cigarettes (including menthol status), e-cigarettes, large and little cigars, and hookah. Lifetime and current use of **marijuana** (combustible, vaporized, and edible) will be assessed via items used in previous research and surveillance studies. Use of cigarillos for blunts will be measured and differentiated from cigarillo tobacco use

CONFIDENTIAL

This material is the property of the University of Pennsylvania. Do not disclose or use except as authorized in writing by the study sponsor

as intended. **Alcohol use** will be measured with epidemiological questions of lifetime, past 30 day use, as well as binge drinking episodes.

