7.5 Analytic Plan

Prior to analyses, standard data cleaning, assumption evaluation, and imputation methodology will be applied. We conservatively assume that 85% of our participants will complete all study visits, and will recruit additional subjects (15%, 13) to replace those who fail to return. The baseline characteristics of subjects who drop out will be examined, with attention to whether there is an association between dropout and flavor preference. Female sex and race will be included in each model. We will also consider baseline variables potentially important to flavor preference (e.g., cigarette smoking status, menthol brand, cigarillo history, prior flavor preference, blunt use, depression, sensation-seeking, cigarillo flavor risk beliefs, and exposure to cigarillo flavor marketing) for inclusion in the multivariate models if bivariate associations with the outcome are $p \leq .20$. Outcomes will be analyzed using general linear models (GLM) with outcome family and links appropriate to each of the respective measures. Where measures are repeated, GLMs will be fitted with generalized estimating equations (GEE).

Aim 1 H1 will determine whether the subjective rewarding value of a sweet flavored cigarillo is greater than that of a non-flavored cigarillo among young adults. H1 will test whether participants report greater subjective rewarding value from a sweet flavored cigarillo than a non-flavored cigarillo. The outcome measure used for analysis is a continuous subjective rating of reward for sweet flavored and non-flavored cigarillos obtained at the first exposure (visit 1). The analysis will use a paired t-test (or GLM equivalent) to assess the effect of flavor. Female sex and race will be included in the model.

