Aim 1 H2 will determine whether the relative reinforcing value of a sweet flavored cigarillo is greater than that of a non-flavored cigarillo among young adults. H2 will test whether participants “work harder” for sweet flavored cigarillo puffs than non-flavored cigarillo puffs (i.e., higher relative reinforcing value) as measured by a choice task. Participants will be given the choice to “work for” sweet flavored puffs at an increasing behavioral cost (more mouse clicks) or non-flavored puffs at a low fixed cost. The outcome variable used for this analysis is a breakpoint representing the highest level of work a participant will perform for a puff of a sweet flavored cigarillo. Flavor is inherent in the breakpoint outcome and will be assessed using a GLM.

Aim 1 H3 will determine whether the absolute reinforcing value of a sweet flavored cigarillo is greater than that of a non-flavored cigarillo among young adults. H3 will test whether participants take more puffs from a sweet flavored cigarillo versus a non-flavored cigarillo during the ad-libitum smoking session. The outcome measure is puff counts of sweet flavored and non- flavored cigarillos, and preference will be estimated as a rate-ratio using negative binomial mixed models.

CONFIDENTIAL

This material is the property of the University of Pennsylvania. Do not disclose or use except as authorized in writing by the study sponsor

Sample Size / Power. The proposed study is a within-subjects design. The sample size is driven by the test for H3. Because we have three experimental outcomes, we will Bonferroni correct our global alpha of 5% for three tests. Informed by the effect size of our prior study investigating e-cigarette flavoring (Cohen's d of 0.5) with a small within-subjects correlation (negative binomial model) of $r=0.13$. A sample of 86 yields 80% power to detect an effect size of 0.5, testing at alpha = 0.017.

8 Risks / Benefits

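### Section 7.4.2 puts cigarillo history, flavor preference and depression in the models outright, but 7.5 admits them only if they pass a p ≤ .20 screen on each outcome; the rules conflict, and H2 is exposed unless covariates are centred.

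*Combined protocol and SAP*

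**What the plan says.** Three places in the combined protocol and SAP bear on which covariates enter the models.

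- **Section 7.4.2 (Covariates)** makes two unconditional commitments. On cigarillo history: "Cigarillo use history (number, flavor preference) will be included in the statistical models". On depression symptoms: "We will measure them and include them as a covariate in the statistical models as depression symptoms may underlie flavor preference".
- **Section 7.5 (Analytic Plan)** forces two covariates: "Female sex and race will be included in each model". Other baseline variables are to be considered "for inclusion in the multivariate models if bivariate associations with the outcome are" p ≤ .20. Nine are named as examples: depression, sensation-seeking, cigarillo history, prior flavor preference, blunt use, cigarette smoking status, menthol brand, flavor risk beliefs and flavor marketing exposure.
- **Section 2.1 (Background)** gives the purpose of adjustment: "We will examine whether these indices of abuse liability remain significant while controlling for other factors that may underlie the preference for flavoring". Section 3 lists this control among the features that make the study new.

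The models differ by hypothesis. For H1, "The analysis will use a paired t-test (or GLM equivalent) to assess the effect of flavor", with sex and race added. For H2 there is one breakpoint per participant: "Flavor is inherent in the breakpoint outcome and will be assessed using a GLM". H3 is a negative binomial mixed model of puff counts. The H2 paragraph gives no null value for the breakpoint and does not say how covariates are coded or centred.

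**The concern.** An analyst who follows 7.4.2 keeps depression, cigarillo history and flavor preference in every model. One who follows 7.5 keeps each of them only when it happens to correlate with the outcome being tested. The 7.5 rule uses the outcome to choose the model, so H1, H2 and H3 can end up adjusted for different things, and the usual standard errors ignore the selection.

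Two things are at stake. The first is the promised statement that the effects hold after control for these factors, since the screen can remove the very factors the protocol names. The second is the H2 test. H2 has no flavor coefficient, so its result is the model intercept, and what an intercept means depends on which covariates are present and how they are coded.

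**Working it through.** **Inputs from the documents.** Sample size 86, the p ≤ .20 screen, nine named candidates, and alpha 0.05/3 = 0.0167, which 7.5 rounds to 0.017. The plan gives no figure of its own for the effect of the screen, so there is none to reproduce.

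**1. The two rules side by side.**

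| Variable | 7.4.2 | 7.5 |
|---|---|---|
| Cigarillo history | in the models | only if p ≤ .20 |
| Flavor preference | in the models | only if p ≤ .20 |
| Depression | in the models | only if p ≤ .20 |
| Sensation-seeking, risk beliefs, marketing exposure | measured | only if p ≤ .20 |

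The conflict covers the first three rows. For the fourth there is none.

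**2. What the screen admits by chance.** Assume nine independent candidates, none related to the outcome.
- Expected number passing: 9 × 0.20 = 1.8.
- P(at least one) = 1 − 0.8⁹ = 0.866.
- P(all three promised variables dropped) = 0.8³ = 0.512.
- Possible adjustment sets per outcome: 2⁹ = 512.

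**3. What the screen drops.** At n = 86 the two-sided p = .20 cut is |r| = 0.1396. On the Fisher z scale this is 0.1405, with standard error 1/√83 = 0.1098. The true correlations below are assumed, since the documents give none.
- r = 0.10 (z = 0.1003): P(pass) = 0.371, so dropped about 63% of the time.
- r = 0.20 (z = 0.2027): P(pass) = 0.716, so dropped about 28% of the time.
- r = 0.30: P(pass) = 0.938, so dropped about 6% of the time.

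**4. H1 and H3.** Section 7.5 fits repeated measures by GEE. In a linear GEE check on one simulated data set, the flavor coefficient was 0.494 (SE 0.149) with zero, two or four person-level covariates. Covariates that are constant within a person do not move a within-person contrast. The same reasoning applies to the H3 rate ratio, which was not simulated.

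**5. H2.** In a linear model the intercept is ȳ − Σ bⱼx̄ⱼ. With mean-centred covariates every x̄ⱼ is zero, so the estimate is the sample mean whatever enters. With 0/1 coding it is a reference-group mean, and screening keeps the coefficients that are large by chance. Simulated type I error at nominal 1.7% (n = 86, sex and race forced, nine independent 50/50 candidates with no true effect, normal outcome, null value 0; 20,000 runs unless noted, Monte Carlo SE about 0.1 point):
- screen, all covariates centred: 1.8%
- all nine fixed in advance, centred: 1.6%
- screen, all covariates uncentred: 6.1%
- screen, sex and race centred, candidates uncentred: about 10% (8,000 runs)
- a further run with uncentred candidates: 10.6% with the screen, 1.7% with a fixed list.

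**The case against.** The strongest reply is that no primary test is shown to be harmed under sensible coding. Much of it stands, and four stronger readings should be set aside.

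- *That all covariates face the screen.* They do not: sex and race are forced into each model.
- *That the screened models are the primary tests.* Section 7.5 speaks of multivariate models and does not say whether these are primary. The H1 paragraph names only sex and race, and Section 2.1 can be read as describing a follow-on analysis. The primary reading is reasonable, because 7.5 describes no separate adjusted analysis, but it is not stated.
- *That the screen inflates H2 error however covariates are coded.* It does not. When centred candidates have real effects, error does rise above nominal, but about equally with no screen: at R² of 0.26 it is 3.6% screened and 3.65% with all nine fixed. The cause is treating sampled covariates as fixed when testing a mean. Selection adds little.
- *That smoking status, sex and race are also promised by 7.4.2, or that smoking status is owed to every model as a stratification factor.* Section 7.4.2 makes no such promise. In Section 4.3 "Order will be stratified by sex and smoking status" concerns only the sequence of exposures at Visit 1, which gives no stratification reason to adjust H2 or H3.

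The 87% also assumes independence. Menthol brand depends on smoking status, and the nine are only examples, so it is a guide and not an exact figure. None of this removes the conflict between 7.4.2 and 7.5.

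**Conclusion.** The plan is wrong as written on this point. Sections 7.4.2 and 7.5 give incompatible rules for cigarillo history, flavor preference and depression, and the 7.5 rule lets each outcome choose its own adjustment set. That undercuts the stated aim of controlling for these factors, since a real but weak one is more likely than not to be dropped at r = 0.10.

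The effect on the hypothesis tests is narrower. The H1 and H3 flavor contrasts are essentially unaffected when fitted as repeated measures. For H2 the size depends on coding the plan leaves open: close to nominal if covariates are centred in a linear model, about 6% to 11% against 1.7% if null candidates are entered as uncentred 0/1 variables. The H2 figures rest on independent binary candidates and a normal outcome, because the documents give no breakpoint distribution. The contradiction itself rests on no assumption. It should be corrected before analysis.

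**What to change.** 1. Delete the p ≤ .20 rule, or confine it to analyses labelled exploratory.
2. Prespecify one adjusted model for all three hypotheses: sex and race (from 7.5) plus cigarillo history, prior flavor preference and depression (from 7.4.2).
3. For H2, either mean-centre the covariates or make the unadjusted test of the mean breakpoint primary and the adjusted model supportive. State the null value in either case. A fixed list alone is not enough: if a covariate truly matters, an uncentred intercept still tests a reference-group mean.
4. State whether the adjusted models are primary or supportive, and reword 7.4.2 and 7.5 so that they agree.

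The cost is wording in the analysis plan and a few degrees of freedom out of 86, some of which may go to covariates that turn out not to matter.

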This material is the property of the University of Pennsylvania. Do not disclose or use except as authorized in writing by the study sponsor

4.4 Laboratory Visit 2

Relative reinforcing value of cigarillo flavoring (RRVF). Participants will arrive at the BBL at 1:00 PM and have their CO measured and provide a urine sample to conduct urine cotinine analysis. Participants who use tobacco (e.g., combustible cigarettes, e-cigarettes, cigars, blunts) or combustible marijuana will have abstained for 10 hours: CO verified < 10 ppm or < 50% of Visit 1's CO value, cotinine verified < Visit 1's cotinine value. In preparation for the assessment of the RRVF, participants will receive an introduction to a validated behavioral choice paradigm, which permits the evaluation of the preference for sweet flavored cigarillo puffs relative to non-flavored cigarillo puffs. Participants will be introduced to and briefly practice the computer task (described below) whereby they will have the chance to earn points for sweet flavored versus non-flavored cigarillo puffs. The goal is to determine the motivation to use a sweet flavored cigarillo rather than to quantify the reinforcing value of specific flavors. The sweet cigarillo flavor with the highest rewarding value (measured in Visit 1) will serve as the flavor for the assessment of the RRVF.

Participants will then begin the validated choice paradigm to assess the RRVF. Assessment of the RRVF will be accomplished by asking the participants to perform work, in the form of moving a computer mouse to hit targets on one of two computer screens to earn points toward either a sweet flavored or a non-flavored cigarillo. Using a concurrent schedule, participants will be told that they can switch from working on one screen to the other as often as they wish. Participants are instructed to move the computer mouse to have the cursor hit the targets (e.g., either a fruit labelled cigarillo or a cigarillo labeled as plain). Consistent with relative reinforcement paradigms, the reinforcement schedule in the non-flavored cigarillo earning screen will remain constant at a fixed ratio FR-25 (25 targets achieved to earn a point) while the reinforcement schedule for the sweet flavored cigarillo will increase (require more effort) with a progressive ratio schedule of PR-25x over 10 trials, such that 25, 50, 75, 100, 125, 150, 175, 200, 225, and 250 targets will have to be achieved to earn a point.

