The computer task will be performed until a participant completes 10 trials and accumulates a total of 10 points from which they will earn either one puff of a non-flavored cigarillo for each point (i.e., up to 10 puffs of a non-flavored cigarillo) or one puff of a sweet flavored cigarillo for each point (i.e., up to 10 puffs of a flavored cigarillo). Participants who are eligible and elect to participate in the study will be required to use the study-provided cigarillos during this portion of the visit in our smoking lab following the RRVF task. Cigarillo puffs will be taken at the end of the procedure to prevent satiation from influencing responding in subsequent trials. RRVF is defined by the breakpoint (highest trial completed across 10 trials to earn puffs for sweet flavored versus non-flavored cigarillo puffs). To ensure that responding in the choice task is based on reinforcer preference rather than departure from the lab, the choice procedure will be followed by a 1- hour wait in the laboratory. After Visit 2 is complete, participants who use tobacco (e.g., combustible cigarettes, e-cigarettes, cigars, blunts) or combustible marijuana will be given instructions to abstain from tobacco products and combustible marijuana 10 hours prior to BBL Visit 3.

4.5 Laboratory Visit 3

Absolute reinforcing value of cigarillo flavoring. The absolute reinforcing value of a sweet flavored cigarillo as measured by an ad-libitum smoking procedure in the lab provides a measure of overall consumption. At this visit, the participant will have the opportunity to self-administer the non-flavored or the sweet flavored cigarillo that they sampled at Visit 1 and chose for the RRVF task at Visit 2. Participants who are eligible and elect to participate in the study will be required to use the study-provided cigarillos during this portion of the visit in our smoking lab. Participants will arrive at the laboratory at 1:00 PM and have their CO measured and provide a urine sample to conduct urine cotinine analysis. Participants who use tobacco (e.g., combustible cigarettes, e-cigarettes, cigars, blunts) or combustible marijuana will have abstained for 10 hours: CO verified < 10 ppm or < 50% of Visit 1's CO value, cotinine verified < Visit 1's cotinine value.

CONFIDENTIAL

This material is the property of the University of Pennsylvania. Do not disclose or use except as authorized in writing by the study sponsor

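### H1 does not say how the two sweet ratings enter the test and leaves out exposure position; averaging the two and adjusting for position would be a cheap gain in precision

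*Combined protocol and SAP*

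**What the plan says.** Section 4.3 (Laboratory Visit 1) sets three exposures: "Participants will take 2 puffs from the non-flavored cigarillo, the fruit-flavored cigarillo, and the cream-flavored cigarillo". On order it says: "The exposure to the three cigarillos will be separated by 20 minutes each, and the order of the three exposures will be counterbalanced". Reward is rated after each exposure, so every participant contributes two sweet ratings and one non-flavored rating.

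Section 7.5 describes the H1 outcome as a "continuous subjective rating of reward for sweet flavored and non-flavored cigarillos obtained at the first exposure (visit 1"), and then: "The analysis will use a paired t-test (or GLM equivalent) to assess the effect of flavor". Sex and race are the named covariates. Exposure position is not named, and no sentence combines the fruit and cream ratings. A general sentence earlier in 7.5 adds: "Where measures are repeated, GLMs will be fitted with generalized estimating equations (GEE"). Section 6.1 says that the values of particular flavors are not of interest.

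For the later visits, section 4.4 says: "The sweet cigarillo flavor with the highest rewarding value (measured in Visit 1) will serve as the flavor for the assessment of the RRVF". Section 4.5 carries the same product forward to Visit 3, as "the sweet flavored cigarillo that they sampled at Visit 1 and chose for the RRVF task at Visit 2". The hypotheses in section 3 and in 7.5 speak only of sweet flavored cigarillos.

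**The concern.** A paired t-test takes two values per person, and Visit 1 produces three. The sweet value could be fruit, cream or their mean, and the text does not settle which. H1 is one of three primary tests with its own Bonferroni share, so its contrast should be fixed before the data are seen.

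What is at stake is mainly precision. Using one sweet rating discards a third of the Visit 1 ratings. Leaving out position puts any systematic drift over the three exposures into the residual variance, although the design has already balanced it.

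A smaller matter concerns H2 and H3. The sweet product there is the better-liked of two, set against a single non-flavored product that nobody selected. A positive result therefore reflects sweet flavoring together with having had two sweet options.

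**Working it through.** **Inputs.** From 7.5: n = 86, three tests at a global 5% (0.05/3 each, printed as 0.017), effect size 0.5, within-subject correlation 0.13. The last two are given for H3, which sets the sample size; no H1 power is stated. Assumptions: the H3 values are borrowed for H1, tests are two-sided (sidedness is not stated), and ratings have equal variances in SD units. Unless noted, both flavors have the same effect.

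**The plan's own figure.** A two-sample t calculation with d = 0.5 and alpha 0.05/3 gives 80.4% power at 86 per condition, which reproduces 86. A paired t with r = 0.13 has standardised effect 0.5/√(2 × 0.87) = 0.379. That needs 76 participants and gives 85.6% power at 86.

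**One sweet rating versus the mean of two.** Let b be the sweet-plain correlation and a the sweet-sweet correlation.

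- One sweet minus plain: variance 2(1 − b).
- Mean of two sweet minus plain: variance (1 + a)/2 + 1 − 2b.

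Power is from the noncentral t with 85 df and d = 0.5:

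| b | a | Variance, one | Power, one | Variance, mean | Power, mean |
|---|---|---|---|---|---|
| 0.13 | 0.13 | 1.74 | 85.6% | 1.305 | 94.5% |
| 0.13 | 0.5 | 1.74 | 85.6% | 1.49 | 91.0% |
| 0.13 | 0.8 | 1.74 | 85.6% | 1.64 | 87.8% |
| 0.3 | 0.13 | 1.40 | 92.8% | 0.965 | 98.8% |
| 0.3 | 0.3 | 1.40 | 92.8% | 1.05 | 98.0% |
| 0.3 | 0.8 | 1.40 | 92.8% | 1.30 | 94.6% |
| 0.5 | 0.5 | 1.00 | 98.5% | 0.75 | 99.8% |
| 0.5 | 0.8 | 1.00 | 98.5% | 0.90 | 99.2% |

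The gain is 2 to 9 points at b = 0.13 and about 1 to 6 points at b = 0.3 to 0.5.

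**Unequal flavors.** Suppose the effects are 0.5 and 0.2, so that the mean effect is 0.35, with b = 0.13. The mean of two then has 66%, 59% or 54% power (a = 0.13, 0.5, 0.8). The stronger flavor alone has 86% and the weaker alone 16%.

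**Position.** With a steady change of s SD per exposure, the contrast shifts by 1.5s one way when the plain product comes first, by 0 when it is second, and by 1.5s the other way when it is third. In a balanced design these shifts average to zero, so there is no bias. They add (2/3)(1.5s)² = 1.5s² to the variance that an unadjusted t-test estimates.

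For s = 0.5 and a = b = 0.13 the estimated variance is 1.305 + 0.375 = 1.68. The standard error is then inflated by √(1.68/1.305) = 1.135, so a critical value of about 2.44 acts like 2.77. The true standardised effect is 0.5√86/√1.305 = 4.06, so power under perfect balance is about Φ(4.06 − 2.77) = 90%.

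Because 86 = 6 × 14 + 2, two participants are left over if six orders are used. Simulation with that imbalance gives, at d = 0.5:

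| Change per exposure | Without position | With position |
|---|---|---|
| none | about 94% | about 94% |
| 0.1 SD | 94.3% | 94.5% |
| 0.25 SD | 93.2% | 94.3% |
| 0.5 SD | 88-89% | about 94% |

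At 0.5 SD per exposure the unadjusted type I error is about 0.7% against a nominal 1.67%; adjusted, it is about 1.7%.

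**GEE route.** In simulation at n = 86, the ordinary sandwich z-test has type I error of about 2.0% and the sandwich with a t reference about 1.8%. The difference is slight.

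**The case against.** The plan already points towards a pooled model: three ratings per person, GEE for repeated measures, and no interest in particular flavors. H1 is also well powered. At d = 0.5 even one sweet rating gives 86%, and three ratings by the same person in one session may well correlate above 0.13, which leaves little to gain. A position effect of 0.5 SD per exposure means 1.0 SD from the first exposure to the third, twice the planning effect, and nothing in the documents suggests it. The selection of the sweet product for H2 and H3 is stated openly in 4.4, with its reason: "The goal is to determine the motivation to use a sweet flavored cigarillo rather than to quantify the reinforcing value of specific flavors".

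All of this stands, and it limits the point to a modest improvement. What remains is that 7.5 permits the better analysis without specifying it.

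Three stronger readings are tempting and should be resisted:

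- A reader might infer that H1 will use each participant's higher-rated sweet flavor, since 4.4 identifies it from the same ratings. That would badly inflate false positives, but the documents never say H1 does so.
- A reader might infer that leaving out position biases H1. Counterbalancing prevents that; the unadjusted test is conservative.
- A reader might infer that choosing the preferred flavor invalidates H2 and H3. The choice is pre-specified and the outcomes are measured afresh at Visits 2 and 3, so the tests are valid. Only the scope of the claim is affected.

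**Conclusion.** The point holds as a low-cost improvement to a valid plan. H1 lacks a stated rule for combining its two sweet ratings and does not use a design factor that the trial already controls.

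Averaging is worth 2 to 9 points of power at a sweet-plain correlation of 0.13, and 1 to 6 points at 0.3 to 0.5. Position adjustment is worth about 0 to 2 points for changes of 0.1 to 0.25 SD per exposure, and more only if drift is as large as 0.5 SD. These sizes rest on the H3 effect size being carried over to H1, two-sided testing, equal variances and, apart from the unequal-flavor check, equal flavor effects. If the flavors differ, the mean can have less power than the stronger flavor alone, but which one is stronger is not known in advance. The mean also fits the stated lack of interest in individual flavors.

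For H2 and H3 the matter is one of wording, and no numerical size is claimed.

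**What to change.** In 7.5, define the H1 contrast as the mean of the fruit and cream ratings minus the non-flavored rating. Compute it per participant and test it at 0.017, adjusting for the position of the non-flavored product. Code the position terms to sum to zero, and center any covariates, so that the intercept is the average contrast. The equivalent is a GEE on all three ratings with product, position, sex and race, testing the same contrast with a robust standard error and a t reference.

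Optionally, state in the H2 and H3 conclusions that the sweet product is the participant's higher-rated of two sweet flavors.

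The cost is a few sentences and two degrees of freedom for position in the per-participant analysis. No new data, visits or participants are needed. If the optional wording is adopted, the H2 and H3 claims become somewhat narrower.
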